## 12.8 Statistical Analysis Plan

In addition to the summarised analysis plan outlined below, a separate document, Statistical Analysis Plan (SAP) for DS107G-05 AD3 will detail all analyses to be performed.

### 12.8.1 Pharmacokinetic Analysis

Plasma concentrations of DGLA will be tabulated and summarised descriptively. Individual and mean plasma concentration-time profiles of DGLA will be presented graphically.

### 12.8.2 Primary variables

The primary variables will be:

- the proportion of patients achieving a vIGA-AD™ score of 0 (clear) or 1 (almost clear) and a decrease of at least 2 points in vIGA-AD™ from baseline to Week 16.
- the proportion of patients achieving EASI-75 ( $\geq 75\%$  improvement from baseline) at Week 16.

Both primary endpoints will be analysed using a Generalised Linear Mixed Model (GLMM) with treatment arm, visit, their interaction treatment-by-visit, and baseline vIGA-AD™ value as factors, and with patient as random effect; this model will especially be used to estimate missing data and the treatment effects at Week 16 taking missing data into account. The primary analysis will be based on the FAS, and repeated for the PPS as a supportive sensitivity analysis. Success in either of the primary endpoints denotes successful proof of efficacy.

If rescue medication is used, the patient will be specified as a non-responder from the time the rescue is used.

The primary statistical analysis assumes “Missing At Random (MAR)” when handling missing data. The treatment effect obtained under the MAR assumption is essentially that which could have been reached if all patients had fully adhered to treatment or, in other words, the effect a patient may expect if they take the medication as directed. This is sometimes known as the ‘de jure’ or ‘efficacy’ estimand. Due to the lack of perfect adherence in practice, the ‘de facto’ or effectiveness treatment effect will also be estimated. This estimand includes assumptions regarding the treatment effects that could be expected to occur when patients discontinue treatment. The *jump to reference* method described by Carpenter *et al.* (2013) will be used to estimate the de facto estimand, using the placebo arm as the reference. This is based on the assumption that patients who discontinue from study drug have no alternative oral treatment option suitable for longer-term use and so their responses are likely to revert to those of the placebo group. An additional sensitivity analysis will evaluate patients who received rescue medication as treatment failures from the visit onwards where rescue treatment started. The sensitivity analyses for missing data will be performed on the FAS only.

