## PROTOCOL SYNOPSIS

STUDY TITLE:	A Randomised, Double-blind, Placebo-controlled Study to Assess the Efficacy and Safety of Orally Administered DS107 in Adult Patients with Moderate to Severe Atopic Dermatitis
SHORT TITLE:	Efficacy and Safety of Orally Administered DS107 in Adult Patients with Moderate to Severe Atopic Dermatitis
PHASE:	II
STUDY DURATION:	20 weeks (Treatment Duration: 16 weeks)
INVESTIGATIONAL PRODUCT:	DS107 Capsules  Placebo
OBJECTIVE:	
Efficacy Objective:
 
 
To compare the efficacy of orally administered DS107 versus placebo, in the treatment of adult patients with moderate to severe Atopic Dermatitis (AD).
 
 
Safety Objective:
 
 
To assess the safety of orally administered DS107 versus placebo, in adult patients with moderate to severe AD.
 

PRIMARY ENDPOINTS:	
 
Proportion of patients achieving a vIGA-AD™ score of 0 (clear) or 1 (almost clear) and a decrease of at least 2 points in vIGA-AD™ in treated population compared to placebo population from baseline at Week 16.
 
Proportion of patients achieving EASI-75 (≥75% improvement from baseline) in treated population compared to placebo population at Week 16.
 
 
Note: Each of the independent primary endpoints will be analysed separately. Success in either of the primary endpoints denotes successful proof of efficacy.

SECONDARY ENDPOINTS:	
 
Proportion of patients achieving a vIGA-AD™ score of 0 (clear) or 1 (almost clear) and a decrease of at least 2 points in vIGA-AD™ in treated population compared to placebo population from baseline to Week 4, 8, 12, 18 and 20 and the change in proportion of patients from Week 16 to Week 18 and 20.
 
Proportion of patients achieving EASI-75 (≥75% improvement from baseline) in treated population compared to placebo population at Week 4, 8, 12, 18 and 20 and the change in proportion of patients from Week 16 to Week 18 and 20.
 

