## 5 STUDY ENDPOINTS

### 5.1 Primary Endpoint

- Proportion of patients achieving a vIGA-ADTM score of 0 (clear) or 1 (almost clear) and a decrease of at least 2 points in vIGA-ADTM in treated population compared to placebo population from baseline at Week 16.
- Proportion of patients achieving EASI-75 ( $\geq 75\%$  improvement from baseline) in treated population compared to placebo population at Week 16.

*Note: Each of the independent primary endpoints will be assessed separately. Success in either of the primary endpoints denotes treatment success.*

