### 12.3 Estimation of Sample Size

In the Phase 2a trial, IGA response rates of 21.6% and 11.8% were observed for DS107 and placebo respectively resulting in a difference in response rates of 9.8%. Due to the prolonged treatment period of 16 weeks, a clinically relevant difference in IGA response rates of 15% was expected for the current study.

Assuming a placebo response rate of 12% and a true response rate difference of 15% at Week 16 and using a two-sided Chi-Square test on a significance of 5%, then 220 evaluable patients (110 patients per treatment arm) will be needed for 80% power to detect this difference as statistically significant. As the following table shows, the number of patients needed for the

discovery of a 15% response rate difference depends also on the placebo response rate shown in the left column of the table as decimal numbers:

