**Number of patients per study group required under the assumptions as follows**  
**Chi-square test, 2 x 2 table, Two Proportions, two-sided.**  
**Sample Size 1 as a function of H1: Proportion 1 and Power.**  
**H1: Proportion 2 - Proportion 1=0,15 Significance Level=0,05 Sample Size 2 / Sample Size 1=1**

H1: Proportion 1 = Response Rate Placebo	Power		
	0,7	0,8	0,9
0,06	63,4	80,3	107,0
0,08	71,2	90,2	120,3
0,10	78,6	99,6	132,8
0,12	85,5	108,4	144,6
0,14	92,0	116,6	155,6
0,16	98,0	124,3	165,9
0,18	103,6	131,4	175,4
0,20	108,8	138,0	184,2

It was assumed that similar estimations apply to the primary endpoint EASI-75.

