## 12.9 Interim Analysis

An interim analysis may be conducted after at least 50% of planned enrolled patients have completed their Week 16 assessments or an early termination visit. The interim analysis will be conducted in accordance with sponsor standard operating procedure (SOP) “Interim Analysis of Clinical Studies”.

An unblinded interim analysis will be performed by an unblinded independent statistician. Interim data and the results of interim analyses will not be accessible by anyone other than the unblinded statistician. The sponsor will remain blinded with procedures in place to ensure the confidentiality of the interim data, as per the sponsor SOP “Interim Analysis of Clinical Studies”.

The unblinded statistician will make one of the following recommendations to the sponsor based solely upon the primary efficacy endpoints:

- Modify the sample size
- Continue the study as originally planned

Further details will be described in an interim statistical analysis plan.

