### 3 Analysis Populations

The assignment of individual patients to the analysis sets will be determined by the members of the BDRM. The patients will be assigned to the following analysis sets before unblinding:

1. Enrolled Set: The Enrolled Set consists of all patients who sign informed consent.
2. Screen Failures: Screen Failures are patients from the Enrolled Set who do not meet the eligibility requirements and are withdrawn from the study prior to randomisation.
3. Randomised Set: The Randomised Set consists of all patients who are randomised to the study.
4. Safety Analysis Set (SAS): The Safety Analysis Set (SAS) consists of all patients who received at least one dose of the medication. SAS is the analysis population for all safety endpoints. Analysis will be done according to the actual treatment patients received.
5. Full Analysis Set (FAS): The Full Analysis Set (FAS) consists of all patients who were randomised to the study and received at least one dose of study medication. FAS is the primary analysis population for efficacy endpoints. Analysis will be done according to the treatment patients were randomised to.
6. Per-Protocol Set (PPS): The Per Protocol Set (PPS) is the subset of FAS who completed the study without any major violations. Protocol violations will be assessed for each patient in a blinded fashion prior to database lock at a Blind Data Review Meeting (BDRM), and the PPS will also be finalised during this meeting. PPS is a supportive analysis population for efficacy endpoints. Analysis will be done according to the treatment patients were randomised to.

For PPS the primary endpoint will only be evaluated in an exploratory sense.

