### 7.2 Efficacy - Primary Endpoint Evaluation

Descriptive statistics will be provided for the two primary endpoints separately with the FAS.

Both primary efficacy endpoints will be analysed as defined in chapter 6.1 with the FAS.

These analyses will be displayed not only overall but also by subgroups as defined in chapter 6.3. The overall analysis will be repeated in an exploratory sense with the PPS.

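### A win on either of two primary endpoints proves efficacy, with no multiplicity rule: at two-sided 5% each, an ineffective DS107 succeeds 3.5% to 4.5% of the time (assumed correlation 0.9 to 0.5) instead of 2.5%

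*Protocol*

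**What the plan says.** Protocol Synopsis, 5.1 and 12.8.2, and SAP 6.1, name two primary endpoints at Week 16: vIGA-AD 0 or 1 with a drop of at least 2 points, and EASI-75. The Synopsis says "Each of the independent primary endpoints will be analysed separately". The decision rule is in Protocol 12.8.2, and again in SAP 6.1: "Success in either of the primary endpoints denotes successful proof of efficacy". Protocol 5.1 words it as "Success in either of the primary endpoints denotes treatment success".

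No significance level stands beside these statements. The only one is in the sample-size sections (Protocol 12.3, SAP 2), where the vIGA-AD calculation is made "using a two-sided Chi-Square test on a significance of 5" per cent. For the second endpoint they add only this: "It was assumed that similar estimations apply to the primary endpoint EASI-75".

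SAP 7.2 adds no rule: "Both primary efficacy endpoints will be analysed as defined in chapter 6.1 with the FAS". Among the primary-endpoint analyses, only the per-protocol repeat is labelled exploratory: "For PPS the primary endpoint will only be evaluated in an exploratory sense". The only sentence on alpha adjustment is in SAP 1.6. It concerns the interim analysis and says that none will be made.

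**The concern.** Two chances to win, each at the full level, give a larger chance of a false claim than one test does. The excess disappears only if the two test statistics are perfectly correlated. The full-analysis-set result carries a claim of proof of efficacy, so this bears directly on the trial's main conclusion.

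Two things are at stake. First, a trial sized on one two-sided 5% test would be decided by a rule with a higher error rate. Because success is never tied to a threshold, the choice could also be made after unblinding. Second, the 80% power quoted in Protocol 12.3 and SAP 2 does not describe the rule that decides the trial.

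**Working it through.** **Inputs.** Two-sided 5%, placebo 12%, difference 15 points (so DS107 27%), 110 evaluable per arm, 1:1 allocation (Protocol 12.2 and 12.3, SAP 1.5 and 2). The documents give no correlation between the endpoints, so 0.5, 0.7 and 0.9 are assumed. Both scales score erythema, induration/papulation and lichenification (Protocol Appendices 3 and 4), which makes the higher values more plausible. EASI-75 rates are taken first as 12% vs 27%, then as 20% vs 35% (an assumption that matches the last row of the sizing table).

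**The plan's own figure.** With pooled rate 0.195,

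n = [1.960·√(2·0.195·0.805) + 0.842·√(0.12·0.88 + 0.27·0.73)]² / 0.15² = 108.3 per arm.

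The table gives 108.4; both round up to 109. Power at 110 per arm is 80.6%. The stated sample size is therefore correct for one endpoint at 5%. At 2.5%, one endpoint has 71.8%.

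**False success with no effect on either endpoint.** Treat the two test statistics as bivariate normal with correlation ρ.

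- Favouring DS107: P = 1 − Φ₂(1.96, 1.96; ρ), which equals 2·0.025 − P(both > 1.96). At ρ = 0.5 this is 0.0500 − 0.0046 = 0.0454; at 0.7, 0.0500 − 0.0083 = 0.0417; at 0.9, 0.0500 − 0.0148 = 0.0352.
- Either direction: P = 1 − P(|z₁| ≤ 1.96 and |z₂| ≤ 1.96).
- Hochberg in favour of DS107: both z > 1.960, or at least one z > 2.241.
- Holm or a 2.5%/2.5% split: at least one z > 2.241. The two rules agree on whether anything is won.

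| Rule | ρ = 0.5 | ρ = 0.7 | ρ = 0.9 | Reference, one test |
|---|---|---|---|---|
| Either at 5%, favouring DS107 | 4.5% | 4.2% | 3.5% | 2.5% |
| Either at 5%, either direction | 9.1% | 8.4% | 7.0% | 5% |
| Hochberg, favouring DS107 | 2.4% | 2.3% | 2.1% | 2.5% |
| Holm or split, favouring DS107 | 2.3% | 2.2% | 1.8% | 2.5% |
| Fixed sequence, favouring DS107 | 2.5% | 2.5% | 2.5% | 2.5% |

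If the endpoints were independent, the first two rows would read 4.94% and 9.75%.

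**Check on binary data.** In 400,000 simulated trials (110 per arm, 12% in both arms, chi-square tests, phi 0.5/0.7/0.9), false success favouring DS107 was 4.7/4.4/3.7%, against 2.6% for one test.

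**Power to win on at least one endpoint, 110 per arm.** For each endpoint the threshold is t = (c·SE₀ − 0.15)/SE₁, where SE₀ is the pooled and SE₁ the unpooled standard error; power = 1 − Φ₂(t₁, t₂; ρ). For 12% vs 27%, SE₀ = 0.0534 and SE₁ = 0.0525, so t = −0.863 at 5% and −0.577 at 2.5%. Hochberg adds the cases where both statistics fall between the 5% and 2.5% thresholds.

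| Rule | 12/27 on both, ρ = 0.5/0.7/0.9 | EASI-75 at 20/35, ρ = 0.5/0.7/0.9 |
|---|---|---|
| Either at 5% | 91.7 / 89.1 / 85.5% | 88.9 / 86.1 / 82.5% |
| Hochberg | 86.7 / 83.7 / 80.1% | 82.9 / 79.7 / 76.0% |
| Holm or split | 85.7 / 82.4 / 77.9% | 81.7 / 78.4 / 74.1% |
| Fixed sequence, vIGA-AD first | 80.6% throughout | 80.6% throughout |

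**The case against.** - **The increase is modest and the trial is Phase II.** The endpoints overlap, so the correlation is probably high; at 0.9 the excess is 3.5% against 2.5%. Strict error control is also asked for less often at this phase. Both points are fair, but 3.5% is still about 1.4 times nominal, and the plan claims proof of efficacy from a formally sized test.
- **Every one-directional figure is below 5%.** True, but the matching reference is 2.5%, the upper half of a two-sided 5% test. On the two-sided scale the figures are 9.1% to 7.0% against 5%. The two scales must not be mixed.
- **The level for the primary tests is never stated.** The figures therefore depend on applying the sample-size level to each endpoint. This qualification stands, but the missing threshold is part of the defect.
- **The plan can still be changed.** Protocol 12.8 leaves the detail to the SAP, and SAP 1 and 5 let the blind data review meeting change methods. That permits a lighter route to a repair, but permission to change is not a rule, and the SAP is already final.
- **Adjusting costs power.** It does. In several scenarios at-least-one-endpoint power falls below 80%, as the table shows.

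**Conclusion.** The concern holds. With each endpoint tested at the only level the documents state, the either/or rule raises the chance of falsely declaring DS107 effective from 2.5% to 4.5%, 4.2% or 3.5% at correlations of 0.5, 0.7 or 0.9. Some excess remains at any correlation below 1. The sample size is arithmetically right; the fault is the missing rule for combining the two tests, and it should be corrected before unblinding.

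The sizes rest on assumed correlations, assumed EASI-75 rates and a single-visit normal approximation, not the planned GLMM. The binary simulation supports the approximation for error rates. None of these assumptions affects the direction of the finding. Any effect of the interim analysis is separate and is not included.

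**What to change.** Pre-specify a rule that controls the error across the two endpoints at two-sided 5%, and put it in the Protocol Synopsis, 5.1 and 12.8.2 and in SAP 6.1. The choice is the sponsor's:

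- **Hochberg**, which keeps the either/or design. Suggested text: *Efficacy is shown if both primary endpoints favour DS107 with two-sided p ≤ 0.05, or if at least one favours DS107 with two-sided p ≤ 0.025.*
- **Holm or a 2.5%/2.5% split**, also either/or, with slightly less power.
- **Fixed sequence**: vIGA-AD at 5%, then EASI-75 at 5% only if vIGA-AD is significant. This keeps the planned 80% (80.6% at 110 per arm) but gives up a win on EASI-75 alone.

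In Protocol 12.3 and SAP 2, state that 80% is the power for one endpoint at 5% (about 72% at 2.5%). Give the at-least-one-endpoint power under the chosen rule, with the assumed EASI-75 rates and correlation. Recommendations at the interim are "based solely upon the primary efficacy endpoints", so the interim SAP should use the same success rule.

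**Cost.** A SAP update and a protocol amendment in both the EU 5.0 and US 5.1 versions. For Hochberg, Holm or a split, the either/or sentence could stand if the SAP defined success, so a SAP amendment may be enough; the fixed sequence contradicts that sentence and needs the protocol changed.

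The loss of at-least-one-endpoint power against the unadjusted rule at 110 per arm, by correlation 0.5/0.7/0.9, is:

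| Rule | 12/27 on both | EASI-75 at 20/35 |
|---|---|---|
| Hochberg | about 5 points | about 6 to 6.5 points |
| Holm or split | 6.0 / 6.7 / 7.7 points | 7.1 / 7.8 / 8.5 points |
| Fixed sequence | 11.1 / 8.5 / 4.9 points | 8.3 / 5.5 / 1.9 points |

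No extra patients are needed to control the error. If the sponsor also wants 80% at-least-one-endpoint power in the least favourable case shown (EASI-75 at 20% vs 35%, correlation 0.9), the same power formula gives about 121 per arm for Hochberg or 126 for a split.

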### 12.8.3 Secondary variables

IGA and EASI-75 responders at other time points will also be analysed using a GLMM model similar to that described in Section 12.8.2.

The efficacy variables and their changes from baseline will be summarized with descriptive statistics per treatment group and visit. This applies to the vIGA-AD™, EASI, NRS scores for pruritus, DLQI, POEM, SCORAD, AIS and PO-SCORAD. Change from baseline endpoints will be analysed using Mixed Model with Repeated Measures (MMRM) with Treatment Arm, Visit and Treatment x Visit Interaction as a factors and baseline value as a covariate, to account for missing data. The secondary efficacy analyses will be based on the FAS only. For vIGA-AD™ as a 5-level ordinal variable, mixed ordinal logistic regression will be used with factors defined as above and IGA at baseline as a factor too.

If rescue medication is used, the patient will be specified as a non-responder from the time the rescue is used

### 12.8.4 Safety variables

The type and frequency of adverse events will be summarised by MedDRA system organ class and preferred term per treatment group. In addition, the number and proportion of patients with at least one adverse event will be summarised per treatment group.

The number and proportion of patients experiencing serious adverse events, adverse events leading to withdrawal and adverse events possibly or probably related to treatment will be summarized per treatment group. The secondary safety analysis will be based on the Safety Analysis Set only.

## 12.9 Interim Analysis

An interim analysis may be conducted after at least 50% of planned enrolled patients have completed their Week 16 assessments or an early termination visit. The interim analysis will be conducted in accordance with sponsor standard operating procedure (SOP) “Interim Analysis of Clinical Studies”.

An unblinded interim analysis will be performed by an unblinded independent statistician. Interim data and the results of interim analyses will not be accessible by anyone other than the unblinded statistician. The sponsor will remain blinded with procedures in place to ensure the confidentiality of the interim data, as per the sponsor SOP “Interim Analysis of Clinical Studies”.

The unblinded statistician will make one of the following recommendations to the sponsor based solely upon the primary efficacy endpoints:

- Modify the sample size
- Continue the study as originally planned

Further details will be described in an interim statistical analysis plan.

## 12.10 Data Collection / Case Report Forms

Data will be collected using a validated electronic data capture (EDC) solution. Electronic Case report forms (eCRFs) will be utilised for recording data from each patient meeting the eligibility criteria and being randomised in the study; and a limited amount of data will be completed for patients who fail to meet eligibility criteria (i.e. screen failures). Electronic access to the CRF will be available to all investigator sites. All study staff responsible for entering data into the eCRF system will be trained prior to the start-up of the study. A personal log-in will be provided for all responsible personnel to allow for an audit trail relating to the study data to be maintained.

All evaluations performed shall be entered in a timely manner into the eCRF by a member of the site staff delegated responsibility for this specific task by the Principal Investigator of the clinical site. It is the responsibility of the Investigator to ensure that the eCRFs are properly completed. The data in the eCRFs should be consistent with the relevant source documents. The Investigator will sign the designated signature fields of the eCRF to confirm that the information on each screen is accurate and complete. All data must be stored in an unidentifiable form treated with strict confidentiality in accordance with applicable data-protection regulations.

Captured data will be monitored electronically and Source Data Verification (SDV) will take place at the site where all information will be verified against the individual patient records. Any inconsistencies will be presented as queries; either as automatically generated queries if raised by the logical data checks of the eCRF system, or by manually generated queries if raised by the data validation checks or the SDV performed by the Data Manager (DM) or the CRA respectively. Queries shall be resolved in a timely manner by a trained member of the site staff.

## 12.11 Data Management

Data will be transmitted electronically into the web based EDC system. Data will be coded according to pre-specified dictionaries and in accordance with the CRO Standard Operating

Procedures (SOP). The handling of data, including data quality control, will comply with all applicable regulatory guidelines.

### **12.12 Protocol Deviations**

Protocol deviations will be captured through site self-reporting, CRA source data verification and data management edit checks and will be recorded by the CRA throughout the study in both the monitoring visit reports and in a centralised log.

